14.3 Appendix C: Ann Arbor staging classification

Not applicable. Please refer to BGJ398XUS04 Protocol Version 02

Stage	Area of involvement
I	Single lymph node group
II	Multiple lymph node groups on the same side of the diaphragm
III	Multiple lymph node groups on both sides of the diaphragm
IV	Multiple extranodal sites or lymph nodes and extranodal disease
X	Bulk disease > 10 cm
E	Extranodal extension or single isolated site of extranodal disease
Class A are patients who experience no B symptoms	
Class B are patients experience unexplained fever of $\geq 38^{\circ}\text{C}$; unexplained, recurrent drenching night sweats; or unexplained loss of >10% body weight within the previous 6 months	

¹ Cotswolds modification of Ann Arbor staging system adapted from 2007 NCCI guidelines for non-Hodgkin's lymphoma

14.4 Appendix D: Rai Staging System ^a

Stage	Area of involvement	Risk Status
0	Lymphocytosis, lymphocytes in blood $>15 \times 10^9/L$ and $>40\%$ lymphocytes in bone marrow	Low
I	Stage 0 with enlarged node(s)	Intermediate
II	Stage 0-1 with splenomegaly, hepatomegaly, or both	Intermediate
III ^b	Stage 0-II with hemoglobin $< 11.0 \text{ g/dL}$ or hematocrit $< 33\%$	High
IV ^b	Stage 0-III with platelets $<100 \times 10^9/L$	High

^a Research originally published in Blood. Rai KR, et al. Clinical staging of chronic lymphocytic leukemia. Blood 1975;46(2):219-234. (c) The American Society of Hematology

^b Immune-mediated cytopenias are not the basis for these stage definitions.

14.5 Appendix E: Criteria for Response assessment in Acute Myeloid Leukemia (based on IWG and Cheson)

Disease assessments will be based on standardized response criteria as defined by the International Working Group (IWG) for AML (Cheson et al 2003).

Response classification in AML at a given evaluation time (Cheson 2003)	
Response category	Definition [#]
Complete remission (CR)	
Bone marrow < 5% blasts no blasts with Auer rods
 
Peripheral blood neutrophils $\geq 1.0 \times 10^9/L$ platelets $\geq 100 \times 10^9/L$ $\leq 1\%$ blasts
 
No evidence of extramedullary disease (such as CNS or soft tissue involvement).
 
Transfusion independent (see Section 7.2.1.4.5).
 
In case all criteria for CR apply and the patient receives platelet and/or neutrophil transfusions, the patient will be assessed as CRi.

Complete remission with incomplete blood count recovery (CRi)	
Bone marrow < 5% blasts no blasts with Auer rods
 
Peripheral blood neutrophils $< 1.0 \times 10^9/L$ and/or platelets $< 100 \times 10^9/L$ $\leq 1\%$ blasts
 
No evidence of extramedullary disease (such as CNS or soft tissue involvement).
 
Transfusion-independent (see Section 7.2.1.4.5). Exception: Platelet and neutrophil transfusions are allowed.

Partial Remission (PR)	
Bone marrow 50% or greater decrease (absolute range 5-25% blasts) < 5% of blasts contain Auer rods
 
Peripheral blood neutrophils $< 1.0 \times 10^9/L$ and/or platelets $< 100 \times 10^9/L$ No evidence of extramedullary disease (such as CNS or soft tissue involvement).

Treatment failure	Treatment failure includes those patients for whom treatment has failed to achieve PR, CRi or CR throughout the treatment.
Relapse from CR or CRi*	Only in patients with a CR or CRi: Reappearance of blasts in peripheral blood ($> 1\%$) OR $\geq 5\%$ blasts in bone marrow OR (Re-)appearance of extramedullary disease

Response classification in AML at a given evaluation time (Cheson 2003)	
Response category	Definition[#]
No response	In case a patient does not achieve CR, CRi, PR or relapse for an individual response assessment.
Unknown	In case the response assessment was not done, the baseline assessment was not done, the assessment was incomplete or was not done within the respective time frame.

[#] If not defined otherwise, all of the criteria apply.
* [Cheson et al \(2003\)](#) does not specify relapse after PR but this may be considered in Phase I or II protocols.

14.5.1 Exploratory AML response categories according to IWG

Response category	Definition
Cytogenetic complete remission (CRc)	All criteria for CR plus no cytogenetic abnormalities
Molecular complete remission (CRm)	All criteria for CRc plus no leukemic cells by RQ-PCR assay

14.6 Appendix F: Criteria for Response assessment in Acute Lymphoblastic Leukemia (based on NCCN Guidelines Version 1.2013)

Response classification in ALL for Blood and Bone Marrow at a given evaluation time	
Response category	Definition[#]
Complete remission (CR)	No circulating blasts or extramedullary disease (such as lymphadenopathy, splenomegaly, skin/gum infiltration, testicular mass, CNS or soft tissue involvement) Trilineage hematopoiesis (TLH) and < 5% blasts neutrophils $\geq 1.0 \times 10^9/L$ platelets $\geq 100 \times 10^9/L$ No recurrence for 4 weeks
Complete remission with incomplete blood count recovery (CRI)	Peripheral blood Recovery of platelets but $< 100 \times 10^9/L$ or neutrophils is $< 1.0 \times 10^9/L$.
Progressive Disease (PD)	Increase of at least 25% in the absolute number of circulating or bone marrow blasts or development of extramedullary disease.
Treatment failure	Treatment failure includes those patients for whom treatment has failed to achieve a CR at the end of treatment
Relapse from CR or CRI*	Only in patients with a CR or CRI: Reappearance of blasts in peripheral blood (> 1%) OR $\geq 5\%$ blasts in bone marrow OR (Re-)appearance of extramedullary disease
No response	In case a patient does not achieve CR, CRI, PR or relapse for an individual response assessment.
Unknown	In case the response assessment was not done, the baseline assessment was not done, the assessment was incomplete or was not done within the respective time frame.

[#] If not defined otherwise, all of the criteria apply.

14.7 Appendix G: Criteria for Response assessment in Chronic Myelogenous Leukemia (based on NCCN Guidelines Version 4. 2013)

Response classification in CML for hematologic, cytogenetic, and molecular evaluation at a given evaluation time	
Response category	Definition [#]
Complete hematologic response (CR) ¹	Complete normalization of peripheral blood counts with leukocyte count < 10 x 10 ⁹ /L platelets < 450 x 10 ⁹ /L No immature cells such as myelocytes, promyelocytes, or blasts in peripheral blood No signs and symptoms of disease with disappearance of splenomegaly
Cytogenetic response ^{2,3}	Complete No Ph-positive metaphases Partial 1% - 35% Ph-positive metaphases Major 0% - 35% Ph-positive metaphases (complete + partial) Minor > 35% Ph-positive metaphases
Molecular response ^{4,5}	Complete No detectable BCR-ABL mRNA by QPCR using an assay with a sensitivity of at least 4.5 logs below standardized baseline. Major ≥ 3 log reduction in international scale of BCR-ABL mRNA
Treatment failure	Treatment failure includes those patients for whom treatment has failed to achieve a complete hematologic response (CR) throughout treatment.
No response	In case a patient does not achieve CR, PR or relapse for an individual response assessment.
Unknown	In case the response assessment was not done, the baseline assessment was not done, the assessment was incomplete or was not done within the respective time frame

[#] If not defined otherwise, all of the criteria apply.

¹ Federl S et al: Chronic myelogenous leukemia: Biology and therapy. Ann Intern Med 1999; 131:207-219.

² A minimum of 20 metaphases should be examined.

³ O'Brien SG, et al: Imatinib compared with interferon and low-dose cytarabine for newly diagnosed chronic-phase chronic myeloid leukemia. N Engl J Med 2003;348:994-1004.

⁴ Hughes TP, et al: Frequency of major molecular responses to imatinib or interferon alfa plus cytarabine in newly diagnoses chronic myeloid leukemia. N Engl J Med 2003;349:1423-1432

⁵ Hughes T, et al: Monitoring CML patients responding to treatment with tyrosine kinase inhibitors; review and recommendations for harmonizing current methodology for detecting BCR-ABL transcripts and kinase domain mutations and for expressing results. Blood 2006;108:28-37

14.8 Appendix H: Criteria for Response assessment in Chronic Lymphocytic Leukemia (based on modified IWG guidelines)

Disease assessments will be based on standardized response criteria as defined by the modified IWG guidelines for CLL. Response in CLL must meet the criteria in both Group A and Group B. Group A criteria defines tumor load. Group B criteria defines the function of the hematopoietic system (or marrow).

Response Definition for Chronic Lymphocytic Leukemia¹

Group A Response for Tumor Burden

Response	Nodal Masses	Organomegaly	Bone Marrow
CR	None > 1.5 cm	No splenomegaly No hepatomegally	Normocellular >30% Lymph. No B lymphoid nodules
CRI	None > 1.5 cm	No splenomegaly No hepatomegally	Hypocellular marrow
PR	Decrease ≥50%	Spleen/Liver decrease ≥50	50% reduction in marrow infiltrate, or B-lymphoid nodules

Group B Response for hematopoietic system²

Response	Platelet count	Hemoglobin	Neutrophils
CR	>100 x 10 ⁹ /L	>11 g/dL	>1.5 x 10 ⁹ /L
CRI	If meets criteria from Group A but does not meet criteria from Group B		
PR	>100 x 10 ⁹ /L or increase ≥50% over baseline	>11 g/dL or increase ≥50% over baseline	>1.5 x 10 ⁹ /L or >50% improvement over baseline
SD	Failure to attain CR/CRI/PR or PD		
Relapsed disease or PD	Appearance of any new lesions; at least one of the above criteria. Isolated progressive lymphocytosis in the setting of reduced lymph node size or organomegaly or improvement in hemoglobin/platelets will not be considered progressive disease		

1. Hallek M, et al. Guidelines for the diagnosis and treatment of chronic lymphocytic leukemia updating the National Cancer Institute-Working Group 1996 Guidelines. Blood 2008; 111:5446-5456

2. All values are without transfusion or hematopoietic growth factors

**14.9 Appendix I: Criteria for Response assessment in Myelofibrosis
(based on modified IWG-MRT guidelines and European
LeukemiaNet (ELN) consensus report)¹**

Response category	Definition
CR	Bone marrow*: Age-adjusted normocellularity; <5% blasts; ≤grade 1 MF [†] and Peripheral blood: Hemoglobin ≥100 g/L and <UNL; neutrophil count ≥ 1 X 10 ⁹ /L and <UNL; Platelet count ≥100 X 10 ⁹ /L and <UNL; <2% immature myeloid cells [‡] and Clinical: Resolution of disease symptoms; spleen and liver not palpable; no evidence of EMH
PR	Peripheral blood: Hemoglobin ≥100 g/L and <UNL; neutrophil count ≥1 X 10 ⁹ /L and <UNL; platelet count ≥100 X 10 ⁹ /L and <UNL; <2% immature myeloid cells [‡] and Clinical: Resolution of disease symptoms; spleen and liver not palpable; no evidence of EMH or Bone marrow*: Age-adjusted normocellularity; <5% blasts; ≤grade 1 MF [†] , and peripheral blood: Hemoglobin ≥85 but <100 g/L and <UNL; neutrophil count ≥1 X 10 ⁹ /L and <UNL; platelet count ≥50, but <100 X 10 ⁹ /L and <UNL; <2% immature myeloid cells [‡] and Clinical: Resolution of disease symptoms; spleen and liver not palpable; no evidence of EMH
Clinical improvement (CI)	The achievement of anemia, spleen or symptoms response without progressive disease or increase in severity of anemia, thrombocytopenia, or neutropenia [§]
Anemia response	Transfusion-independent patients: a ≥20 g/L increase in hemoglobin level Transfusion-dependent patients: becoming transfusion-independent [^]
Spleen response#	A baseline splenomegaly that is palpable at 5-10 cm, below the LCM, becomes not palpable ^{**} or A baseline splenomegaly that is palpable at >10 cm, below the LCM, decreases by ≥50% ^{**} A baseline splenomegaly that is palpable at <5 cm, below the LCM, is not eligible for spleen response A spleen response requires confirmation by MRI or computed tomography showing ≥35% spleen volume reduction
Symptoms response	A ≥50% reduction in the MPN-SAF TSS ^{††}
Progressive disease ^{‡‡}	Appearance of a new splenomegaly that is palpable at least 5 cm below the LCM or A ≥100% increase in palpable distance, below LCM, for baseline splenomegaly of 5-10 cm or A 50% increase in palpable distance, below LCM, for baseline splenomegaly of >10 cm or Leukemic transformation confirmed by a bone marrow blast count of ≥20% or A peripheral blood blast content of ≥20% associated with an absolute blast count of ≥1 X 10 ⁹ /L that lasts for at least 2 weeks

Response category	Definition
Stable disease	Belonging to none of the above listed response categories
Relapse	No longer meeting criteria for at least CI after achieving CR, PR, or CI, or Loss of anemia response persisting for at least 1 month or Loss of spleen response persisting for at least 1 month
Recommendations for assessing treatment-induced cytogenetic and molecular changes	
Cytogenetic remission	At least 10 metaphases must be analyzed for cytogenetic response evaluation and requires confirmation by repeat testing within 6 months window CR: eradication of a preexisting abnormality PR: $\geq 50\%$ reduction in abnormal metaphases (partial response applies only to patients with at least ten abnormal metaphases at baseline)
Molecular remission	Molecular response evaluation must be analyzed in peripheral blood granulocytes and requires confirmation by repeat testing within 6 months window CR: Eradication of a pre-existing abnormality PR: $\geq 50\%$ decrease in allele burden (partial response applies only to patients with at least 20% mutant allele burden at baseline)
Cytogenetic/molecular relapse	Re-emergence of a pre-existing cytogenetic or molecular abnormality that is confirmed by repeat testing

¹ Tefferi et al. (2013) Revised response criteria for myelofibrosis: International Working (IWG-MRT) and European LeukemiaNet (ELN) consensus report Group-Myeloproliferative Neoplasms Research and Treatment. Blood; 2013 122: 1395-1398
 
EMH, extramedullary hematopoiesis (no evidence of EMH implies the absence of pathology- or imaging study-proven nonhepatosplenic EMH); LCM, left costal margin; UNL, upper normal limit.
 
[†]Grading of MF is according to the European classification
 
Thiele et al. European consensus on grading bone marrow fibrosis and assessment of cellularity. Haematologica. 2005;90:1128.
 
It is underscored that the consensus definition of a CR bone marrow is to be used only in those patients in which all other criteria are met, including resolution of leukoerythroblastosis. It should also be noted that it was a particularly difficult task for the working group to reach a consensus regarding what represents a complete histologic remission.
 
[‡]Immature myeloid cells constitute blasts + promyelocytes + myelocytes + metamyelocytes + nucleated red blood cells. In splenectomized patients, $< 5\%$ immature myeloid cells is allowed.
 
[§]See above for definitions of anemia response, spleen response, and progressive disease. Increase in severity of anemia constitutes the occurrence of new transfusion dependency or a ≥ 20 g/L decrease in hemoglobin level from pretreatment baseline that lasts for at least 12 weeks. Increase in severity of thrombocytopenia or neutropenia is defined as a 2-grade decline, from pretreatment baseline, in platelet count or absolute neutrophil count, according to the Common Terminology Criteria for Adverse Events (CTCAE) version 4.0. In addition, assignment to CI requires a minimum platelet count of $\geq 25\,000 \times 10^9/L$ and absolute neutrophil count of $\geq 0.5 \times 10^9/L$.
 
Applicable only to patients with baseline hemoglobin of < 100 g/L. In patients not meeting the strict criteria for transfusion dependency at the time of study enrollment (see as follows), but have received transfusions within the previous month, the pre-transfusion hemoglobin level should be used as the baseline.
 
[^]Transfusion dependency before study enrollment is defined as transfusions of at least 6 units of
	

Response category	Definition
	packed red blood cells (PRBC), in the 12 weeks prior to study enrollment, for a hemoglobin level of <85 g/L, in the absence of bleeding or treatment-induced anemia. In addition, the most recent transfusion episode must have occurred in the 28 days prior to study enrollment. Response in transfusion-dependent patients requires absence of any PRBC transfusions during any consecutive "rolling" 12-week interval during the treatment phase, capped by a hemoglobin level of ≥ 85 g/L.
	#In splenectomized patients, palpable hepatomegaly is substituted with the same measurement strategy.
	**Spleen or liver responses must be confirmed by imaging studies where a $\geq 35\%$ reduction in spleen volume, as assessed by MRI or CT, is required. Furthermore, a $\geq 35\%$ volume reduction in the spleen or liver, by MRI or CT, constitutes a response regardless of what is reported with physical examination.
	††Symptoms are evaluated by the MPN-SAF TSS. ¹ The MPN-SAF TSS is assessed by the patients themselves and this includes fatigue, concentration, early satiety, inactivity, night sweats, itching, bone pain, abdominal discomfort, weight loss, and fevers. Scoring is from 0 (absent/as good as it can be) to 10 (worst imaginable/as bad as it can be) for each item. The MPN-SAF TSS is the summation of all the individual scores (0-100 scale). Symptoms response requires $\geq 50\%$ reduction in the MPN-SAF TSS.
	##Progressive disease assignment for splenomegaly requires confirmation my MRI or computed tomography showing a $\geq 25\%$ increase in spleen volume from baseline. Baseline values for both physical examination and imaging studies refer to pretreatment baseline and not to post-treatment measurements.

14.10 Appendix J: Criteria for Response assessment in polycythemia vera (based on modified IWG-MRT guidelines and European LeukemiaNet (ELN) consensus report)¹

Response categories	Required criteria
Complete remission	
A. Durable resolution of disease-related signs including palpable hepatosplenomegaly, large symptoms improvement[†] AND
 
B. Durable peripheral blood count remission, defined as Ht lower than 45% without phlebotomies; platelet count $\leq 400 \times 10^9/L$, WBC count $< 10 \times 10^9/L$, AND
 
C. Without progressive disease, and absence of any hemorrhagic or thrombotic event, AND
 
D. Bone marrow histological remission defined as the presence of age-adjusted normocellularity and disappearance of tri-linear hyperplasia, and absence of $>$grade 1 reticulin fibrosis

Partial remission	
A. Durable resolution of disease-related signs including palpable hepatosplenomegaly, large symptoms improvement[†] AND
 
B. Durable peripheral blood count remission, defined as Ht lower than 45% without phlebotomies; platelet count $\leq 400 \times 10^9/L$, WBC count $< 10 \times 10^9/L$, AND
 
C. Without progressive disease, and absence of any hemorrhagic or thrombotic event, AND
 
D. Without bone marrow histological remission defined as persistence of tri-linear hyperplasia.

No response	Any response that does not satisfy partial remission
Progressive disease	Transformation into post-PV myelofibrosis, myelodysplastic syndrome or acute leukemia [‡]

Molecular response is not required for assignment as complete response or partial response.
 
Molecular response evaluation requires analysis in peripheral blood granulocytes. Complete response is defined as eradication of a preexisting abnormality. Partial response applies only to patients with at least 20% mutant allele burden at baseline. Partial response is defined as $\geq 50\%$ decrease in allele burden.
 
WBC, white blood cell.
 
Large symptom improvement (≥ 10-point decrease) in MPN-SAF TSS.²
 
For the diagnosis of post-PV myelofibrosis, see the IWG-MRT criteria³; for the diagnosis of myelodysplastic syndrome and acute leukemia, see WHO criteria.
	

¹ Barosi G, et al; Revised response criteria for polycythemia vera and essential thrombocythemia: an ELN and IWG-MRT consensus project. *Blood* 2013;121: 4778-4781

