6.2 Overall Response Rate (ORR)

Overall response is determined by investigator assessment for each tumor assessment in the study. For subjects with solid tumors (other than lymphoma) the assessment criteria will be RECIST 1.1 and will include responses of CR and/or PR; for lymphoma, Cheson criteria will be used; for hematologic tumors, other appropriate hematological response criteria will apply. The number and percentage of subjects for different categories of overall response (e.g., for solid tumors – CR, PR, SD, PD, Not Evaluable) will be provided for solid tumors (non-lymphoma), lymphoma (if applicable), and each hematological tumor type (if applicable). Ninety-five percent (95%) exact confidence intervals (CIs) will be provided for the response rate(s) (e.g., for solid tumors – CR and/or PR) as well. For cohorts with at least 10 subjects, overall responses will be summarized separately. Components of tumor assessments (e.g., for solid tumors – target lesion response, non-target lesion response, new lesion [yes/no]) will also be listed. In addition, Cancer Antigen-125 (CA-125) (if applicable) in the assessment of ovarian cancer response, Prostate-specific Antigen (PSA) (if applicable) in the assessment of prostate cancer will be listed.

The above analyses will be performed for the FAS.

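### Leukaemia response rows kept for ongoing patients conflict with neighbouring rows: AML PR requires low counts, ALL CRi omits the blast conditions, and the CLL CR marrow limit and PD row do not fit the rest of their table

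*Protocol*

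**What the plan says.** Protocol 7.2.1.4 assigns AML, ALL and CLL response to Appendices E, F and H and keeps these assessments for ongoing patients, with no new leukaemia enrolment. Protocol 10.4 and 10.5.1 send haematologic response for the primary and key secondary endpoints to the appendices. SAP 6.2 tabulates response for "each hematological tumor type (if applicable") and supplies no criteria of its own.

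- **Appendix E (AML).** CR and CRi both need fewer than 5% marrow blasts. PR needs a fall of at least half, to 5–25% blasts, together with neutrophils below 1.0 "and/or platelets $< 100 \times 10^9/L$ No evidence of extramedullary disease". A footnote makes all criteria in a row apply unless stated otherwise. A patient who fits no category is No response, and one who never reaches PR, CRi or CR is a Treatment failure.
- **Appendix F (ALL).** The CR row sets marrow-blast, circulating-blast and extramedullary conditions. The CRi row mentions only platelets recovering but below 100, or neutrophils below 1.0 (×10⁹/L). Treatment failure means not reaching CR.
- **Appendix H (CLL).** "Response in CLL must meet the criteria in both Group A and Group B". The CR marrow cell is "Normocellular >30% Lymph. No B lymphoid nodules". The PR marrow cell is "50% reduction in marrow infiltrate, or B-lymphoid nodules". The relapse/PD row begins "Appearance of any new lesions; at least one of the above criteria".
- **Appendix D (Rai).** More than 40% marrow lymphocytes is part of stage 0 disease.

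**The concern.** These rows are the operative scoring rules for any leukaemia patient already in the Full Analysis Set. If a row contradicts its neighbours, the category depends on whether the assessor follows the print or silently corrects it. That choice may differ between sites and cannot be reproduced from the protocol.

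What is at stake is who counts as a responder in ORR, and therefore who enters DOR. The CLL PD row also bears on who has a progression event in PFS.

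**Working it through.** The plan gives no figure to reproduce. The check applies each row literally, with criteria joined by AND as the AML and ALL footnotes and the CLL two-group rule require, and classifies test patients. Counts are ×10⁹/L.

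**AML.** Baseline blasts are 60% and current blasts 10%, with no Auer rods, circulating blasts or extramedullary disease. The fall is (60 − 10)/60 = 83%, and 10% lies within 5–25%. CR and CRi are ruled out because 10% is not below 5%. Only the PR count condition then decides:

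| Neutrophils | Platelets | Category as printed |
|---|---|---|
| 0.3 | 20 | PR |
| 0.9 | 99 | PR |
| 1.0 | 100 | No response |
| 2.5 | 200 | No response |

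The marrow is the same in every line, and better counts give the worse category. If the state persists, Treatment failure also applies.

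**ALL.** Take 60% marrow blasts, 30% circulating blasts, extramedullary disease, neutrophils 0.4 and platelets 30. The neutrophil branch of the printed CRi row is met on its own (0.4 < 1.0). The findings in the relapse row (circulating blasts above 1%, marrow blasts of at least 5%, extramedullary disease) are met at the same time. The AML CRi row states its marrow, blast and extramedullary conditions in full, so the gap is visible within the protocol. A genuine CRi patient would also fall under ALL Treatment failure, because that row recognises only CR. The AML equivalent recognises CRi.

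**CLL.** Nodes, organs, nodules, cellularity and blood counts are all held at CR level:

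| Marrow lymphocytes | Reduction in infiltrate | Category as printed |
|---|---|---|
| 10% | 85% | PR |
| 29% | 50% | PR |
| 30% | 50% | PR |
| 31% | 50% | CR |
| 45% | 30% | CR |
| 60% | 5% | CR |

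The CR cell sets a floor and no ceiling. The PR cell rewards a reduction, and Appendix D treats more than 40% as a disease finding. The three cannot all hold.

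The categories above the PD row in Appendix H are CR, CRi, PR and SD. None contains a worsening threshold, so the row's back-reference has no target.

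**Size of one reclassification.** The number of leukaemia patients is not given, so group size n is an assumption. One changed response moves a group's ORR by 100/n points: 33 at n = 3, 25 at n = 4 and 10 at n = 10. Three and four are the minimum added-cohort sizes in Appendix R (14.1.1.2 and 14.1.1.0). Ten is the size at which SAP 6.2 reports a cohort separately.

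**The case against.** The strongest objection is that the stronger readings of these rows do not survive their context. Much of it stands.

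- A reader might infer that florid ALL would be scored as a response. The documents do not support that as intent. The category is named as a complete remission, its platelet clause speaks of recovery, and the relapse row speaks of blasts reappearing, which presupposes clearance. The row is incompletely drafted.
- A reader might infer that a CLL patient whose marrow clears becomes a non-responder. With the infiltrate halved, that patient is still PR, and ORR counts PR or better. In the other direction, scoring an infiltrated marrow as CR also needs normal cellularity, no lymphoid nodules, no enlarged nodes or organs, and recovered counts. That combination is narrow.
- A reader might infer that meeting a CLL response threshold, such as platelets above 100, equals progression. The same row excludes isolated lymphocytosis when haemoglobin or platelets improve, so the wording is vague but does not equate response with progression.
- The CLL point turns on one symbol in text extracted from PDF. The AML and ALL points do not.
- Section 7.2.1.4 also names published criteria as the standard. They are not available here, so actual misclassification is unproven.
- No document shows that a leukaemia patient was enrolled or scored. The responses reported in the Amendment 3 rationale are all in the six solid tumours.

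None of this removes the AML conflict. Nor does it make unwritten corrections by assessors a substitute for consistent criteria.

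**Conclusion.** The point holds as an internal inconsistency in rows that are still in force, with limited reach.

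- **AML PR** is the clear error for ORR: better counts with the same marrow turn PR into No response.
- **ALL CRi** is incomplete and, as printed, overlaps with relapse. Its effect on ORR assumes that CRi counts as a response, which the documents do not state.
- **CLL CR** mainly misranks CR against PR, subject to checking the sign on the source page.
- **CLL PD** lacks a usable worsening criterion.

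The exposure is ORR and DOR for any leukaemia patient already treated, and PFS only through the CLL PD row. The six re-opened solid-tumour cohorts are unaffected. The Bayesian CBR analysis is affected only if a leukaemia cohort met minimum enrolment and had a control rate, and Table 14-1 lists none. A general claim that active disease scores as response and better responders as failures would go too far: the second half fits only AML.

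**What to change.** Check the CLL CR marrow cell against the source page. Then reconcile the AML PR row, the ALL CRi and Treatment failure rows, and the CLL CR and PD rows with their neighbouring rows and with the guidelines the protocol cites. Print the reconciled criteria in Appendices E, F and H.

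No threshold is proposed here. The clinical content belongs to the cited criteria, and progression also ends treatment under protocol 4.1.1.

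State in SAP 6.2 which leukaemia categories count as a response, including CRi. Report how many leukaemia patients were treated and re-check any response already scored. If there were none, one sentence saying so closes the point. The cost is a few corrected table rows and a review of existing assessments, with no new data.
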